Date: 4/14/16

Principal Investigator: [name]

Application Number: IRB0007923

NCT: 02674477

Title: Treatment Engagement With Technology-assisted Treatment

1. Abstract

Technology-assisted treatment, or TAT (e.g., online modules, mobile applications), shows promise for innovative assessment, prevention, and treatment of substance use disorders (SUDs). The widespread access to TAT makes it a potentially cost-effective and innovative option available for delivery in multiple settings. To date, there have been no published studies that investigate whether TAT is effective in patients with SUDs in addition to another psychiatric illness (dual diagnosis patients). Thus, we plan to pilot a computerized cognitive behavioral therapy (CBT) program called the Therapeutic Education System (TES) in dually diagnosed inpatients and allow them access to the program as outpatients as well. Our hypothesis is that those assigned to TES will have better program retention and outpatient attendance than those assigned to treatment as usual (TAU), because the patients using TES may be more engaged in the process of problem recognition and problem solving with regard to their mental health and substance use problems. This research will be valuable to better understand the treatment needs of this dually diagnosed population, including ways to keep them engaged in care.

2. Objectives

We propose to conduct a controlled study assessing: 1) whether exposure to TES during hospitalization is acceptable to dually-diagnosed patients, and 2) whether TES use affects post-discharge treatment retention.

3. Background

Several computerized contingency management and cognitive-behavioral interventions for SUDs have shown efficacy in single-site clinical trials, and TES has been shown to have efficacy in a clinical trial involving multiple community-based addiction treatment programs¹⁻⁴. We surveyed inpatients on two hospital-based dual diagnosis units at the Johns Hopkins Hospital (JHH) to assess their interest in, access to, and experience with TAT, as well as preferences for content and implementation. Preliminary data suggest that despite most patients having no previous TAT exposure, they would welcome TAT during and after hospitalization, and would consider it helpful. Some patients preferred face-to-face therapy alone, suggesting that TAT should not completely replace these services.

4. Study Procedures

a. Study design, including the sequence and timing of study procedures

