Many patients discharged from the MBU receive referral appointments to the Community Psychiatry Programs (CPPs) at JHH or Johns Hopkins Bayview Medical Center (JHBM) for psychiatric care, and many also go to the Broadway Center (the primary outpatient site operated by JHH for substance use treatment). When possible and appropriate, these will be the preferred referral sites for study participants, as is current practice. Patient involvement with outpatient care (i.e. enrollment) at either CPP can be tracked via the Electronic Medical Record. We will also track patient retention at other mental health and substance use treatment programs that patients may be referred to, by contacting the program directly with the patient's consent.

b. Study duration and number of study visits required of research participants.

At the time of study enrollment and prior to discharge from the hospital, patients in both groups will be administered a survey that assesses acceptability of their inpatient and outpatient treatment, self-efficacy and health-related quality of life, drug and/or alcohol relapse, and the experimental group will also be assessed for their acceptability of TES.

Since the length of inpatient stay and other factors may vary across patients, we will not attempt to dictate the number of TES modules that should be completed but will attempt to ensure that all TES participants have experience with the program before they leave and will track and record the amount of usage during the inpatient stay.

c. Blinding, including justification for blinding or not blinding the trial, if applicable.

Blinding is not possible as those getting the intervention will be using the computer program whereas those that are in the control group will not.

- d. Justification of why participants will not receive routine care or will have current therapy stopped.

All patients will receive treatment as usual, so no routine care will be stopped.

- e. Justification for inclusion of a placebo or non-treatment group.

The TAU group will not receive the TES intervention, though they will still receive the typical treatment on the unit. A comparison of the survey responses and post-discharge program adherence of the TES and TAU groups will provide information as to whether the TES intervention is helpful.

- f. Definition of treatment failure or participant removal criteria.

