As noted above, TES has shown efficacy in clinical trials among patients with SUDs in community-based addiction treatment programs. The two-group randomized design with TAU as the comparison condition was selected to provide a clinically relevant evaluation of TES when used as a supplement to TAU. Since acceptability and effects on post-discharge follow up care are of primary interest in this pilot trial rather than mental health or drug use outcomes, any imbalance in amount of therapy delivered should not be relevant.

- b. Justification and safety information if FDA approved drugs will be administered for non-FDA approved indications or if doses or routes of administration or participant populations are changed.

N/A

- c. Justification and safety information if non-FDA approved drugs without an IND will be administered.

The Therapeutic Education System (TES) is not a physical/mechanical device; but it is a software program that is accessed through the Internet on any PC or Mac computer using a specific username and password. Our research subjects will use it through a site-specific license, so that their information is separate from other TES users. TES does not pose any significant risk to subjects as it is not an implant, is not used for sustaining human life, does not present potential for serious risk to the health, safety or welfare of a subject and will not be used substantially in diagnosing, curing, or mitigating disease. It is a treatment, but it is not the primary treatment modality that will be employed with patients who enroll in this pilot study. As therapy, it will only be used adjunctively to treatment as usual in the form of education, in a supervised manner. Thus, TES does not meet the definition for a significant risk device, but is a nonsignificant risk device.

7. Study Statistics

- a. Primary outcome variable.

Acceptability of TES, via both self-report and actual usage, will constitute the primary outcome measure for the randomized design portion of the study.

- b. Secondary outcome variables.

The enrollment rate for outpatient mental health and substance abuse treatment at 30 days post-discharge, and patient satisfaction regarding the hospital stay among both groups will be investigated as secondary outcomes.

- c. Statistical plan including sample size justification and interim data analysis.

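### Objective 2 asks about post-discharge retention and attendance, but the only post-discharge care outcome is an undefined 30-day enrollment rate, so that objective is at best weakly answered

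*Combined protocol and SAP*

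**What the plan says.** The question is put in terms of retention and attendance. Section 1 (Abstract) hypothesises that "those assigned to TES will have better program retention and outpatient attendance" than the usual-treatment group. Section 2 gives two objectives: "whether exposure to TES during hospitalization is acceptable to dually-diagnosed patients", and "whether TES use affects post-discharge treatment retention". Section 6.a adds that "acceptability and effects on post-discharge follow up care are of primary interest in this pilot trial".

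The outcomes are in section 7. Acceptability of TES, by self-report and usage, is primary (7.a). The secondary outcomes (7.b) are "The enrollment rate for outpatient mental health and substance abuse treatment at 30 days post-discharge" and satisfaction with the hospital stay. Section 7.c names no analysis for the 30-day rate.

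Section 4.a describes how post-discharge care is followed. For the CPPs: "Patient involvement with outpatient care (i.e. enrollment) at either CPP can be tracked via the Electronic Medical Record". For the rest: "We will also track patient retention at other mental health and substance use treatment programs", by contacting the program with the patient's consent. Section 4.e uses a further term, adherence, for the post-discharge comparison. None of enrollment, retention, attendance or adherence is defined.

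**The concern.** Enrolling in a program, staying in it and turning up for visits are three different things. The plan asks about the last two and lists an outcome named after the first. A team that follows 7.b exactly will report an enrollment rate against a hypothesis about retention and attendance.

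The error can run either way. If TES helps patients stay in care without changing who signs up, an entry measure will miss it. If TES only raises sign-up, a statement about retention would go beyond what was measured. The trial is unblinded (4.c), so leaving the meaning of the 30-day rate open also lets it be settled after results by arm are known. Section 6.a places post-discharge care among the matters of primary interest, so the point is not peripheral even though the outcome is secondary.

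**Working it through.** **The plan's own figure.** There is none for this outcome. The only power statement (7.c: 50 per group, effect size 0.313, alpha 0.05, power 0.87) concerns acceptability ratings. It reproduces at 0.873 for a two-sided two-sample t-test if 0.313 is Cohen's f (d = 2 × 0.313 = 0.626). Read as Cohen's d, it gives about 0.34. Nothing below depends on it.

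**Step 1: the sections side by side.**

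| Place | Term used |
|---|---|
| 1, hypothesis | retention and attendance |
| 2, Objective 2 | retention |
| 4.a, CPPs (medical record) | involvement, glossed as enrollment |
| 4.a, other programs (by contact) | retention |
| 4.e, arm comparison | adherence |
| 7.b, outcome | enrollment rate at 30 days |

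Attendance appears in the hypothesis and in no outcome. Retention appears in the objective and in one branch of the tracking, but not in section 7.

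**Step 2: what 7.b can mean.**

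- Ever enrolled by day 30: entry into care only.
- Still enrolled at day 30: retention at a single time point, without visits kept. A patient can remain on a program's roll and attend nothing.

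The text does not choose between them.

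**Step 3: why the choice matters.** The documents give no enrollment or retention rates, so these inputs are assumed. Let e be the proportion enrolling, equal in both arms, and r the proportion of enrollees still in care at day 30. Retention is e × r.

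- Control: 0.60 × 0.50 = 0.30. TES: 0.60 × 0.75 = 0.45. Retention difference: 15 points.
- Ever-enrolled reading of 7.b: 0.60 − 0.60 = 0 points.
- Still-enrolled reading: 0.45 − 0.30 = 15 points, provided the roll reflects who has stayed.

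With the same 25-point change in r and e between 0.30 and 0.70, the retention difference runs from 0.30 × 0.25 = 7.5 points to 0.70 × 0.25 = 17.5 points. The ever-enrolled reading shows 0 throughout.

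**Step 4: what a correct measure could show.** With 50 per arm and 30% versus 45%:

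- SE = sqrt(0.30 × 0.70/50 + 0.45 × 0.55/50) = sqrt(0.00915) = 0.096, so the 95% CI is about ±1.96 × 0.096 = ±19 points.
- Two-sided power at 0.05 is 0.34.
- Over assumed control rates of 30% to 70%, the difference detectable with 80% power is about 22 to 28 points.

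A well-defined outcome would therefore still support estimation rather than a firm test.

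**The case against.** The strongest reply is that the 30-day rate may well mean still enrolled at day 30. That is a usable, if crude, retention measure, and the 0-point result in the illustration then disappears. This stands as far as it goes: the example holds only on the ever-enrolled reading. It does not settle the matter, because the plan does not say which is meant and neither reading captures attendance.

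It can also be said that 4.a uses loose synonyms. It says retention will *also* be tracked elsewhere, which suggests one thing followed through two sources, and 7.b has a single term for all programs. That is possible. Nothing states that two constructs will be pooled, so the supportable claim is that the measure may differ by program, not that it will.

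Finally, this is a secondary outcome, without its own power calculation, in a self-described pilot. That limits the weight of the point. It does not make a retention conclusion from enrollment data sound.

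A reader might go further in two directions that the documents do not support:

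- *The trial cannot answer its own question.* Objective 1 has a matching primary outcome, and enrollment is the only listed outcome for post-discharge care, not for the trial.
- *The mixed terms bias the arm comparison because referral site is not a stratification factor.* Randomisation follows the inpatient baseline assessment, while referral is described for patients leaving the unit, so site is apparently settled after allocation and could not readily be a factor. Randomisation gives no expected imbalance in site unless TES itself alters referral, which nothing suggests. Section 4.a also indicates that patients may go both to a CPP and to the Broadway Center, so a calculation assigning one site per patient would not fit, and the plan gives no rates for it.

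**Conclusion.** The point holds for Objective 2 and the abstract hypothesis. Retention and attendance are the stated question, the one post-discharge care outcome is an undefined enrollment rate, no reading of it measures attendance, and the tracking terms differ between programs. Objective 2 is at best weakly answered. Objective 1 is untouched.

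The size cannot be derived from the documents. The contrast of 15 points with 0 rests on assumed rates, on equal enrollment in the two arms and on the ever-enrolled reading. It shows that the definition can decide the result; it does not estimate the error. This should be corrected before the data are analysed, but it does not undermine the trial as a whole.

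**What to change.** In 7.b, replace or supplement enrollment with one retention and attendance outcome, applied identically at every program and in both arms. For example: at least one outpatient visit attended and still in treatment at day 30 (yes/no), with the number of visits attended by day 30 as support. Define still in treatment in one sentence, and say how mental health and substance use programs combine for a patient referred to both.

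Take the data from the medical record for the CPPs and from the program contact already planned for the others, asking for the same items. State the denominator, including how patients who discharge themselves against advice with no appointment are counted; 7.d takes them out of further participation but does not say whether they enter the 30-day rate. In 7.c, report the difference in proportions with a 95% CI. Keep enrollment as a descriptive step towards retention.

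If only enrollment is kept, say whether it means ever or still enrolled, reword the abstract hypothesis and Objective 2 to enrollment, and make no claim about retention or attendance.

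The cost is protocol wording and one or two extra items per record look-up or call. The reported rate will probably be lower than an enrollment rate.

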This project will be conducted on the Motivated Behaviors Unit (MBU), which is an inpatient dual diagnosis treatment service located on Meyer 3. Standard MBU treatment comprises a psychiatrist-led interdisciplinary team as well as face-to-face group counseling for substance use and skills for improving general mental health. There will be no change to the routine care (treatment at usual [TAU]) provided to patients on the service.

Informed consent will be obtained from each potential participant. This process will include permission to contact participants following discharge, and to review their hospital chart for necessary information such as demographics and diagnoses. Volunteers will then undergo a baseline assessment on acceptability of TAT, using an instrument developed for this project, as well as an assessment of self-efficacy and health-related quality of life using the NIH Toolbox Self-Efficacy Survey⁵, and the Medical Outcomes Study 36-item Short-Form Health Survey (SF-36),⁶ respectively. Study participants will be randomized using an urn design method to receive either TAU or TAU plus TES. Patients will be stratified based on ethnicity, gender and whether

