TES acceptability will be rated on a scale of 0-10, and will be analyzed by mean and SEM. Comparison of hospital ratings will be performed using a paired t-test. The hypothesis is that the TES group will have significantly higher ratings than the TAU group. Based on a previous study of acceptability of TES compared to standard treatment⁷, a power analysis with alpha = 0.05

indicates that 50 persons per group is adequate to demonstrate an effect size of 0.313, where estimated power is 0.87.

d. Early stopping rules.

Those patients who leave against medical advice without a follow up appointment will be excluded from further participation in the study and thus can be included in analysis of any surveys completed during their stay, but not the post-discharge surveys. Any participants who no longer meet inclusion/exclusion criteria (e.g. MMSE score falls to 25 or below) will be removed from the study.

8. Risks

a. Medical risks, listing all procedures, their major and minor risks and expected frequency.

N/A

b. Steps taken to minimize the risks.

N/A

c. Plan for reporting unanticipated problems or study deviations.

These will be reported promptly to the IRB if any arise, though this is unexpected.

d. Legal risks such as the risks that would be associated with breach of confidentiality.

Given the content of the questionnaires there is little anticipated legal risk.

e. Financial risks to the participants.

N/A

9. Benefits

a. Description of the probable benefits for the participant and for society.

The participants in the TES group will benefit from participating in this study through increasing the skill set needed to work in recovery. Patients such as those participating in this study who have a substance use disorder as well as another psychiatric illness will benefit from the findings of this study as it will help us to better understand the needs of this population and whether this treatment will help them to be more engaged in their recovery. Similarly, this research will help the field and society through advancing what is currently known about psychiatric services for treating dually diagnosed patients, and thus working to reduce the mental and physical health complications, financial burden and disability caused by addiction in the community.

10. Payment and Remuneration

a. Detail compensation for participants including possible total compensation, proposed bonus, and any proposed reductions or penalties for not completing the protocol.

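### Section 7c names only a paired t-test, but its hypothesis compares two independently randomised groups; the power of 0.87 should be restated for that comparison once the meaning of 0.313 has been checked

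*Combined protocol and SAP*

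**What the plan says.** The trial has two parallel arms. Section 4a: "Study participants will be randomized using an urn design method to receive either TAU or TAU plus TES". Randomisation is stratified by ethnicity, gender and whether an opioid is the main drug; no matching of individuals into pairs is described. Section 6a confirms the structure: "The two-group randomized design with TAU as the comparison condition was selected". Section 4e sets out the intended contrast: "A comparison of the survey responses and post-discharge program adherence of the TES and TAU groups will provide information".

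Section 7c gives one test: "Comparison of hospital ratings will be performed using a paired t-test". The next sentence reads: "The hypothesis is that the TES group will have significantly higher ratings than the TAU group". The power statement, which takes its effect size from a cited earlier study and uses alpha 0.05, "indicates that 50 persons per group is adequate to demonstrate an effect size of 0.313, where estimated power is 0.87".

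Several ratings could be meant:
- Section 4b: "At the time of study enrollment and prior to discharge from the hospital, patients in both groups will be administered a survey". That survey includes how acceptable patients find their inpatient and outpatient care.
- Section 4b adds that "the experimental group will also be assessed for their acceptability of TES", so this rating exists in one arm only.
- Section 4a gives all volunteers a baseline rating of the acceptability of technology-assisted treatment, repeated before discharge.
- Section 7b lists satisfaction with the hospital stay, in both groups, as a secondary outcome.

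**The concern.** A paired t-test needs a natural link between the two values in each pair. TES and TAU patients have no such link, so the only test in the plan cannot answer the only hypothesis that section 7c states. An analyst following the text would have to choose another test after the fact, or run a within-patient test that answers a different question.

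The power sentence adds a second difficulty. Next to a t-test, an unlabelled effect size of 0.313 is easily read as a difference in standard deviation units between the arms. A reader who does so believes that the trial has 87% power for about half the between-group difference to which 87% corresponds at 50 per group.

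**Working it through.** **Inputs.** Alpha 0.05, 50 per group, effect size 0.313 and power 0.87 (section 7c); a total of at least 100 participants (section 5). Metric, sidedness, SD and rating are not given, so the readings are tried in turn. Power is from the noncentral t or F distribution.

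**1. Does the test fit the hypothesis?** The hypothesis contrasts two groups of different people, formed by urn randomisation with stratification. Stratification balances the groups; it does not create pairs. The only pairs that the documents describe are two ratings from the same patient, at enrolment and before discharge. A paired test on those measures change over time, either in one arm or pooled over both. Neither version estimates TES minus TAU.

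**2. Reproducing 0.87.**
- *Cohen's f, two groups, N = 100.* Noncentrality = N × f² = 100 × 0.313² = 9.797 on F(1, 98). Power = **0.873**. This equals a two-sided two-sample t-test with d = 2 × 0.313 = 0.626. One-sided, the same effect gives 0.928, so this reading matches only if two-sided.
- *Standardised within-patient change, paired test on all 100.* Noncentrality = 0.313 × √100 = 3.13, df 99. Power = **0.873** two-sided, 0.928 one-sided.

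**3. Readings that do not give 0.87.**
- *Between-group d, 50 per group.* Noncentrality = 0.313 × √(50/2) = 1.565, df 98. Power = **0.341** two-sided, **0.464** one-sided.
- *Paired test with 50 pairs, standardised change 0.313.* Noncentrality = 0.313 × √50 = 2.213, df 49. Power = 0.583 two-sided, 0.705 one-sided.

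A d of 0.313 can be brought to 0.87 with a further assumption, for example baseline adjustment at 50 per group with a correlation of about 0.865. The documents give no correlation.

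**4. What 50 per group delivers for TES against TAU.** Solving for d at 87% power, df 98:

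| Test | Standardised difference |
|---|---|
| Two-sided | 0.623 |
| One-sided | 0.558 |

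The 95% confidence interval for the difference has half-width t(0.975, 98) × √(2/50) = 1.984 × 0.2 = 0.397 SD.

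**The case against.** The strongest defence is that the paired test was meant for within-patient change. Both arms are surveyed twice in hospital, and a two-sided paired test on all 100 participants with a standardised change of 0.313 gives 0.873, which agrees with the plan's figure. That reading makes the named test legitimate and the arithmetic sound. It stands as a possibility, but it does not supply a test of TES against TAU, and the 0.87 would then say nothing about that hypothesis.

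A second defence is that the power sentence speaks of persons per group, which suggests a two-group calculation, and that Cohen's f also gives 0.873. This too stands. On that reading the figure is right and lacks only a label.

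A reader might go further and infer that 0.87 is an error and that the pilot really has 34% power. The documents do not support that. It follows only if 0.313 was a between-group d, and the metric is not stated. The effect size comes from a cited study that was not available here. Nor do the documents support the opposite inference, that f must have been used, since a second reading gives the same figure.

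Finally, this is a pilot and the repair is one of wording. That bears on how heavily the point weighs, not on whether the test fits.

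**Conclusion.** The mismatch between test and hypothesis is plain in the text and rests on no assumption: the comparison is between independent groups, the only named test is paired, and no other is given. It should be corrected.

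The power sentence cannot be interpreted as written, but it is not shown to be wrong. With 50 per group, the power for TES against TAU at 0.313 ranges from 0.34 (d, two-sided) to 0.87 (f, two-sided), and to 0.93 if f is taken one-sided. These figures assume equal groups of 50, a common SD and an unadjusted comparison.

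The rating is also open. At least three are collected in both arms; acceptability of TES itself is not among them and cannot carry the between-group hypothesis.

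**What to change.** 1. Replace the test sentence in section 7c with: *Ratings in the TES and TAU groups will be compared with an independent two-sample t-test.* List any enrolment-to-discharge paired t-test as a separate within-patient analysis.
2. Name the rating. It must be one that both groups give, for example acceptability of inpatient and outpatient care (section 4b), acceptability of technology-assisted treatment (section 4a) or satisfaction with the hospital stay (section 7b).
3. State sidedness, and state power for that test: *With 50 per group, a two-sided two-sample t-test at alpha 0.05 has 87% power for a standardised mean difference of about 0.62* (about 0.56 if one-sided).
4. Check the original calculation.
   - (a) If 0.313 was Cohen's f, two-sided, 0.87 stands; label it f = 0.313 (d about 0.63).
   - (b) If it was a standardised within-patient change on all 100 participants, 0.87 is not the power for TES against TAU; replace it with the statement in step 3.
   - (c) If it was a between-group d, restate the power as 34% two-sided (46% one-sided) and report the difference with a 95% confidence interval (half-width about 0.40 SD).

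The cost is a few reworded sentences and one check: no extra patients, visits or data, and no change in sample size. The downside is that the stated power becomes less favourable under (c), and under (b) 0.87 can no longer be quoted for the TES-versus-TAU hypothesis at 0.313.

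### Section 7d excludes patients who leave against advice with no appointment, and nothing in the plan keeps them in the 30-day enrolment rate

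*Combined protocol and SAP*

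**What the plan says.** Section 7d (early stopping rules) states: "Those patients who leave against medical advice without a follow up appointment will be excluded from further participation in the study". The only analysis consequence it gives is that they "can be included in analysis of any surveys completed during their stay, but not the post-discharge surveys".

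Section 7b lists as a secondary outcome "The enrollment rate for outpatient mental health and substance abuse treatment at 30 days post-discharge", without a denominator. Section 4e bases the evaluation on "A comparison of the survey responses and post-discharge program adherence of the TES and TAU groups", so surveys and adherence are two separate comparisons; 7d speaks to the first and is silent on the second.

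The enrolment outcome does not depend on surveys. Section 4a says that enrolment at the two community psychiatry programs "can be tracked via the Electronic Medical Record", and for other sites: "We will also track patient retention at other mental health and substance use treatment programs that patients may be referred to", with the patient's consent. The consent process described in Section 4a includes "permission to contact participants following discharge, and to review their hospital chart", and Section 5 requires agreement to contact with later providers.

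The abstract frames the hypothesis on retention and attendance by assigned arm. No section defines an analysis population, or a rule for missing or untraced enrolment status.

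**The concern.** A patient excluded from further participation would ordinarily be neither tracked nor counted afterwards, and 30-day enrolment is observed only after discharge. Unless the plan says otherwise, the rate would then be computed among those who left in the planned way or with an appointment.

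That conditions the comparison on an event after randomisation. Patients know their arm, TES is meant to increase engagement, and leaving without an appointment is nearly the same thing as not enrolling. If TES keeps some reluctant patients on the unit, they enter the TES denominator while their counterparts in TAU disappear from theirs.

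Enrolment is a secondary outcome in a pilot. It is, however, the only outcome in Sections 7a and 7b that bears on the abstract's hypothesis about retention and attendance after discharge, and Section 6a names effects on follow-up care as a main interest. The primary outcome, acceptability, is not at issue here.

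**Working it through.** The plan gives no enrolment rate, departure rate or power for this outcome, so there is no figure of its own to reproduce. The power of 0.87 in Section 7c concerns the acceptability rating and plays no part. All rates below are assumptions.

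**Inputs**
- s = 0.60: enrolment among other patients (assumed).
- pC, pT: departure against advice without an appointment in TAU and TES (assumed, 5% to 20%).
- eL: enrolment among leavers (assumed, 0% to 20%).
- r: enrolment among patients who stay only because of their arm (assumed, 20% or 60%).
- n per arm: 65 from about 130 accrued, or 50 from the planned minimum of 100 (Section 5; equal arms assumed).

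**Level, equal departure p.** True rate = (1−p)s + p·eL; the rate after exclusion is s.
- eL = 0: at p = 5/10/15/20% the true rate is 57/54/51/48%, reported as 60%.
- eL = 20%: the true rate is 58/56/54/52%, reported as 60%.
- The overstatement is p(s−eL). Over s = 50% to 60%, eL = 0 to 20% and p = 5% to 20%, it runs from 0.05×0.30 = 1.5 points to 0.20×0.60 = 12 points.

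**Difference, TES lowers departure.**
- All randomised: TES = (1−pC)s + (pC−pT)r + pT·eL; TAU = (1−pC)s + pC·eL.
- Leavers excluded: TES = [(1−pC)s + (pC−pT)r]/(1−pT); TAU = s.

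For pC = 0.20, pT = 0.10, r = 0.20, the true difference is (0.50 + 0.10eL) − (0.48 + 0.20eL) = 0.02 − 0.10eL. After exclusion it is 0.50/0.90 − 0.60 = 0.556 − 0.600 = −0.044.

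| TAU vs TES departure | r | True difference at eL = 0 / 10 / 20% (points) | After exclusion (points) |
|---|---|---|---|
| 20% vs 10% | 20% | +2 / +1 / 0 | −4.4 |
| 20% vs 10% | 60% | +6 / +5 / +4 | 0 |
| 10% vs 5% | 20% | +1 / +0.5 / 0 | −2.1 |
| 10% vs 20% | 20% | −2 / −1 / 0 | +4.4 |
| 10% vs 20% | 60% | −6 / −5 / −4 | 0 |
| 5% vs 10% | 20% | −1 / −0.5 / 0 | +2.1 |

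The last three rows are the case where TES raises departure; the arms swap and the signs reverse.

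**Difference, equal departure.** With no effect among stayers, exclusion leaves the difference unbiased. If TES lifts stayers from 60% to 70% and leavers enrol alike in both arms, the true difference is (1−p)×10 = 9.5/9.0/8.5/8.0 points at p = 5/10/15/20%, reported as 10.

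**Scale.** 95% half-width = 1.96·√(2×0.25/n) = 17.2 points at n = 65 and 19.6 at n = 50.

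**Is counting untraced leavers as not enrolled any better?** If all leaver enrolment were missed, the error in the difference is |pC−pT|·eL: at 20% vs 10%, 0.10×0.10 = 1 point or 0.10×0.20 = 2 points. Exclusion errs by 5.4 or 4.4 points (r = 20%) and by 5 or 4 points (r = 60%). The errors are equal where, for r = 20%, 0.0644 − 0.10eL = 0.10eL, so eL = 0.322; and for r = 60%, 0.06 − 0.10eL = 0.10eL, so eL = 0.30.

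**The case against.** The strongest objection is that 7d states its own analysis consequence, and that consequence is confined to surveys. Enrolment comes from records and providers, needs nothing further from the patient, and rests on permissions given at entry. On that reading the outcome is untouched and the plan merely omits a denominator. The text allows this reading but never states it. Section 4f, for a different kind of removal, keeps only data gathered before removal, so it gives no help. Two analysts could compute different rates from the same plan. The consent form is not available, so whether it covers tracking after exclusion must be checked.

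The magnitudes are also open to challenge. Section 5 allows for losing about 30 of 130 (23%) for all reasons. A 20% departure in both arms would use 26 of those 30, and 20% vs 10% about 19.5 (13 + 6.5), although 7d covers only one kind of loss. The allowance is not a forecast, but it makes the larger cases look like upper bounds, with the 5% vs 10% case at least as relevant. Nothing in the documents shows that departure differs by arm. The break-even also moves with s: when r = s it is s/2, so 25% if others enrol at 50%.

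Finally, a leaver with no referral may enrol at a site that the team never contacts, so the remedy has an error of its own. That stands, and is why the fix includes a sensitivity analysis. The denominator question for patients removed for loss of eligibility is separate and is not covered here.

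**Conclusion.** The concern holds. Section 7d as written leads to dropping these patients from the 30-day enrolment rate, and no other section keeps them in. Their exclusion from the rate is an inference, not an explicit instruction.

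Each arm's rate is overstated whenever leavers enrol less often than others, which is plausible for patients without an appointment but not shown in the documents. The arm difference can be biased in either direction if departure differs by arm, by about 4 to 6 points in the 20% vs 10% cases and about 1 to 3 points if the gap is 5 points (for r = 20%, 2.1 to 3.1 points; for r = 60%, 0.05×(0.60−0.20) = 2 to 0.05×0.60 = 3 points when leavers enrol at 0 to 20%, and less if they enrol more often). It is slightly inflated if departure is equal and TES works among stayers, and unbiased if departure is equal and TES has no effect among them.

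The shifts lie inside the sampling error of this pilot, but they are systematic. The point should be fixed, with medium confidence, because the actual size is unknown.

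**What to change.** Leave the survey handling in 7d as planned, and add one or two sentences:

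- These patients stay in the 30-day enrolment analysis under their randomised arm.
- Status is taken from the electronic record and from program contact as far as consent permits; no enrolment found counts as not enrolled.
- Departures against advice are reported by arm, and the enrolment comparison is given as a risk difference with a 95% CI.
- Two sensitivity analyses: (a) exclude leavers; (b) vary the assumed enrolment of leavers with no record from 0% up to the rate among other patients, separately by arm.

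Section 4f and the rule on loss of eligibility are unchanged.

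The cost is a check of the consent wording and a record check for about 3 to 13 patients per arm (65×0.05 = 3.25; 65×0.20 = 13). Reported rates will look lower, and some enrolment may be missed. Excluding leavers would be the more accurate choice only if they truly enrol above about 30%, half the rate assumed for others; sensitivity analysis (b) covers that case.
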